5.3.2 Bleeding

The main safety outcome of the study is bleeding. Subjects with bleeding or suspected bleeding will undergo confirmatory laboratory or other testing (ultrasound [US], CT, MRI, etc.) and an (S)AE CRF must be completed. All clinically overt bleeding events that lead to medical treatment or evaluation, or discontinuation of study medication must be submitted for adjudication. Major and clinically relevant non-major bleeding will be adjudicated by CEC according to definitions specified in the CEC charter.

Acute clinically overt bleeding is defined as new onset, visible bleeding or signs or symptoms suggestive of bleeding with confirmatory imaging techniques which can detect the presence of blood (eg, US, CT, MRI).

The definition of major bleeding described below is adapted from the International Society on Thrombosis and Hemostasis (ISTH) definition.

Major bleeding event is defined as a bleeding event that is:

- Acute clinically overt bleeding accompanied by one or more of the following:
 - A decrease in hemoglobin (Hb) of 2 g/dL or more
 - A transfusion of 2 or more units of packed red blood cells
 - Bleeding that occurs in at least one of the following critical sites:
 - ◆ Intracranial
 - ◆ Intra-spinal
 - ◆ Intraocular (within the corpus of the eye; thus, a conjunctival bleed is not an intraocular bleed)
 - ◆ Pericardial
 - ◆ An operated joint and requires re-operation or intervention
 - ◆ Intramuscular with compartment syndrome
 - ◆ Retroperitoneal
- Bleeding that is fatal

Clinically relevant non-major bleeding event is defined as a bleeding event that is:

- Acute clinically overt bleeding

- Does not satisfy additional criteria required for the bleeding event to be defined as a major bleeding event
- Requires medical treatment or evaluation, or leads to discontinuation of study medication.

Minor bleeding event is defined as any adjudicated bleeding event that does not meet the criteria for Major Bleeding or Clinically Relevant Non-Major Bleeding.

Fatal Bleeding Event is defined as a bleeding event that the CEC determines is the primary cause of death or contributes directly to death.

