8.4.3 Safety Analyses

For safety analyses, separate summaries taking into account length of treatment (28 or 90 days) and randomization phase (randomization prior to or after DMC safety interim analysis decision) will be provided.

The proportion of subjects with the composite of major bleeding and CRNM bleeding, and additional bleeding endpoints such as all bleeding events (including major bleeding, clinically relevant non-major bleeding and minor bleeding) and intracranial hemorrhage during the treatment period will be summarized by treatment. Point estimates and 95% CIs for event rates of each of above safety endpoints will be presented by treatment, together with point estimates and 95% CIs for the difference of event rates between each BMS-986141 arm and placebo. A single variable based on study change points (length of treatment [28 or 90 days] and randomization phase [randomized prior to or after DMC safety interim analysis decision]) will be included as a stratum in the calculation of the CIs.

The number and percent of subjects with at least one adverse event will be summarized for each treatment group, including summaries of AEs, SAEs, AEs leading to discontinuation, and AEs of special interest. Summaries will include the number of subjects with events by specified system organ classes and preferred terms. All endpoint events reported by the investigator as AEs (serious or non-serious) will be reported in the safety analyses, regardless of whether the event was confirmed by adjudication. The number and percent of subjects with marked laboratory abnormalities will be similarly presented.

Values and changes from baseline at each scheduled time point for clinical laboratory parameters, vital signs, and ECG will be summarized by treatment group using descriptive statistics.

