All AEs will be coded and grouped into Preferred Terms (PT) by System Organ Class (SOC), using the most current available version of Medical Dictionary for Regulatory Activities (MedDRA). Summaries of AEs will use the version of MedDRA that is current at the time of database lock. All recorded adverse events will be listed and tabulated by SOC, PT, treatment and overall. Values for ECGs, vital signs, and clinical laboratory test results will be summarized by treatment. Abnormal results for ECG, vital signs and clinical laboratory tests that fall outside the pre-specified criteria will also be listed and summarized. In addition, ECG readings will be evaluated by the Investigator and abnormalities, if present, will be listed.

7.6.1 *Major Bleeding and Clinically Relevant Non-Major Bleeding*

The proportion of subjects with adjudicated bleeding events which occur on or after the first dose of study treatment and within 4 days after the last dose of study treatment will be summarized by treatment. Point estimates and 95% exact CIs for event rates of each of the below bleeding endpoints will be presented by treatment, together with point estimates and 95% exact CIs for the difference of event rates between each BMS-986141 arm and placebo. The following bleeding endpoints will be analyzed using these methods.

- The proportion of subjects with the composite of adjudicated major bleeding and CRNM bleeding
- The proportion of subjects with all reported bleeding
- The proportion of subjects with intracranial hemorrhage

All adjudicated bleeding events will be listed. In addition, the proportion of subjects with confirmed major bleeding or clinically relevant non-major bleeding events occurring during the treatment period will be summarized by treatment group for each of the following factors.

- Stroke severity (based on National Institutes of Health Stroke Scale NIHSS) at study entry
 - NIHSS Score of 0 (No stroke symptoms)
 - NIHSS Score of 1-4 (Minor stroke)
 - NIHSS Score of 5-15 (Moderate stroke)
- Lacunar infarct at study entry
 - Yes
 - No

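### As defined, Minor bleeding is close to an empty class, and SAP 7.6.1 does not settle whether all reported bleeding means adjudicated or investigator-reported events

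*Protocol*

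**What the plan says.** Protocol 5.3.2 sets four rules that have to work together.

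- Recording: "Subjects with bleeding or suspected bleeding will undergo confirmatory laboratory or other testing (ultrasound [US], CT, MRI, etc.) and an (S)AE CRF must be completed".
- Submission: "All clinically overt bleeding events that lead to medical treatment or evaluation, or discontinuation of study medication must be submitted for adjudication".
- CRNM: an acute, clinically overt, non-major bleed that meets this condition: "Requires medical treatment or evaluation, or leads to discontinuation of study medication".
- Minor: "Minor bleeding event is defined as any adjudicated bleeding event that does not meet the criteria for Major Bleeding" or CRNM.

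The same section names only two classes when it describes the work of the clinical events committee (CEC): "Major and clinically relevant non-major bleeding will be adjudicated by CEC according to definitions specified in the CEC charter".

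Elsewhere Minor is treated as a working category. The synopsis lists it as one of three classes, and Protocol 8.4.3 plans an analysis of "all bleeding events (including major bleeding, clinically relevant non-major bleeding and minor bleeding".

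The safety objectives in both documents (Protocol 1.3.3, SAP 3.3) refer to all reported bleeding. SAP 7.6.1 introduces its bleeding endpoints with "The proportion of subjects with adjudicated bleeding events which occur on or after the first dose of study treatment" and a cut-off 4 days after the last dose. It then lists three endpoints: the adjudicated Major plus CRNM composite, all reported bleeding, and intracranial hemorrhage. Each gets event rates with exact 95% CIs, and differences from placebo with exact 95% CIs.

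**The concern.** To be Minor, a bleed must first be adjudicated. The condition that sends a bleed to adjudication is almost the condition that makes it CRNM. The filter at the door therefore removes nearly everything the Minor class is meant to hold, and the bleeds it turns away have no class.

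This reaches a stated safety objective. One programmer may follow the SAP 7.6.1 lead-in and use adjudicated events only. Another may follow the bullet and use every reported bleed. The two would produce different rates, differences and intervals for the same endpoint. Under the first reading, the endpoint that should show low-grade bleeding by dose, for an antithrombotic added to ASA, would add little to the composite beside it.

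**Working it through.** The plan states no figure for this point, so the check is logical.

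**Step 1. Inputs.** All come from Protocol 5.3.2. Each bleed has four yes/no attributes: acute, clinically overt, trigger met (treatment, evaluation or discontinuation), and Major criterion met.

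- Must be submitted = overt AND trigger.
- Major = acute AND overt AND Major criterion.
- CRNM = acute AND overt AND not Major AND trigger.
- Minor = submitted AND not Major AND not CRNM.

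**Step 2. Enumeration.** Four attributes give 2 × 2 × 2 × 2 = 16 combinations. The 8 that are not overt are neither submitted nor classified. The 8 that are overt fall out as follows.

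| Acute | Trigger met | Major criterion | Must be submitted | Class |
|---|---|---|---|---|
| yes | yes | yes | yes | Major |
| yes | yes | no | yes | CRNM |
| no | yes | yes or no (2 combinations) | yes | Minor |
| yes | no | yes | no | meets Major |
| yes | no | no | no | none |
| no | no | yes or no (2 combinations) | no | none |

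Four combinations must be submitted. The two acute ones are Major and CRNM, and neither is Minor. Minor arises only in the two judged overt but not acute. Even that is generous, because fatal bleeding is listed as a Major criterion in its own right, so a fatal non-acute bleed would leave Minor too. A few more could enter because submission turns on what the bleed *leads to*, whereas CRNM partly turns on what it *requires*, and the CEC may judge the second differently from the site.

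**Step 3. Effect on all reported bleeding.** No document gives a bleeding rate or a share of bleeds below the trigger, so the following is illustration only. Take 100 reported bleeds. Assume a share b of 30% to 70% lies below the trigger, and that the CEC downgrades a share q of 0% to 10% of submitted bleeds to Minor.

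- Submitted = 100 × (1 − b): 70 at b = 30%, 30 at b = 70%.
- Adjudicated Minor = submitted × q: from 0 up to 70 × 0.10 = 7.
- Major + CRNM = submitted × (1 − q): from 30 × 0.90 = 27 up to 70.
- All bleeding, adjudicated only: 30 to 70.
- All bleeding, as reported: 100.

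Under the adjudicated-only reading, all bleeding exceeds Major + CRNM by at most 7 bleeds in 100. Under the reported reading it exceeds it by 30 to 73. These are counts of bleeds. The endpoint counts subjects, so they do not convert directly to event rates.

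**Step 4. Protocol-required testing.** Section 5.3.2 calls for confirmatory testing of every bleed or suspected bleed. If that testing counts as medical evaluation, every acute overt bleed meets the trigger and every non-major one becomes CRNM. Minor is then nearly empty for a different reason, and CRNM, a component of the primary safety composite, grows. The text does not say which reading applies.

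**The case against.** Four points on the other side have weight.

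- The submission rule is a minimum. A reader might infer that only triggered bleeds can be adjudicated, but the text does not say so. Protocol 7.2 has the CEC adjudicating bleeding with no trigger and leaves its full role to a charter that is not part of these documents. This stands. What can be said is that neither document describes another route.
- A reader might infer that all bleeding necessarily collapses onto Major + CRNM. The documents do not support that. The objective and the SAP 7.6.1 bullet say reported, and the endpoint lists in Protocol 8.3.4 and SAP 4.5 attach the word adjudicated to major bleeding but not to all bleeding events. Protocol 8.4.3 says the analysis includes the three classes, which need not be exhaustive. The collapse follows only if the SAP lead-in governs, or if that three-class list is read as complete. The conflict itself remains.
- A reader might infer that minor bleeds are lost. They are not. Every bleed goes on an (S)AE CRF, Protocol 8.4.3 keeps investigator-reported endpoint events whether or not adjudication confirmed them, and SAP 7.6.4 tabulates all AEs by treatment group. What those tables lack is a pooled bleeding line with differences from placebo and CIs.
- The affected item is an additional safety endpoint, reported by estimation without a hypothesis test. This is correct and limits the consequence.

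**Conclusion.** The point holds in a limited form. As Protocol 5.3.2 is written, Minor bleeding is close to empty and acute overt bleeds below the trigger without a Major criterion have no class, although the synopsis and Protocol 8.4.3 rely on Minor as a category. This assumes that the unseen CEC charter does not widen submission. SAP 7.6.1 gives two incompatible sources for an endpoint that serves a stated objective.

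The size cannot be derived from the documents. Any count of subjects missing from the all-bleeding rate would rest on an outside bleeding rate and on the adjudicated-only reading.

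The primary safety endpoint does not use the Minor definition. Only the separate question of what counts as medical evaluation could move it. The wording should be settled before unblinding, because bleeding is the main safety outcome and the choice of source changes reported between-arm differences.

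**What to change.** - In Protocol 5.3.2, drop the requirement that a Minor bleed be adjudicated. Define Minor as any reported bleeding event not adjudicated as Major or CRNM.
- In SAP 7.6.1, take adjudicated out of the general lead-in and attach it to the Major/CRNM composite. Build all reported bleeding from adjudicated Major/CRNM events plus all bleeding events on the (S)AE CRF, using a bleeding-term list fixed before unblinding. State the source for the intracranial hemorrhage line as well, since the endpoint lists attach no adjudication label to it.
- Reconcile the testing required for every bleed with the medical-evaluation wording in the CRNM criterion and the submission trigger, and say whether that testing alone meets them.

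The cost is protocol and SAP wording and a term list. The data are already collected on the (S)AE CRF, so no new collection or adjudication is needed. The drawback is that this secondary safety line will contain some events that no committee has reviewed, which a footnote should state.

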5.3.3 Physical Examination

- A complete physical examination should include general appearance, head, eyes, ears, nose, throat, neck, cardiovascular, lungs, abdomen, lymph nodes, extremities, neurological, skin, and musculoskeletal
- The individual performing the physical examinations must be licensed by state law (or applicable local law) to perform this procedure

5.3.4 Vital Signs

Vital signs (blood pressure and heart rate) will be recorded during the Screening visit and at each study visit during the treatment period. Vital signs scheduled at the same visit as blood samples or ECG should be completed before blood is drawn, ECG is collected or any medication is administered.

5.3.5 Physical Measurements

Physical measurements, including height (Screening only) and weight will be measured at the Screening visit and at each study visit during the treatment period.

5.3.6 Electrocardiograms

A 12-lead ECG will be recorded at Screening and at the end of treatment period visits.

5.3.7 Laboratory Test Assessments

A local/central laboratory will perform the analyses and will provide reference ranges for these tests. All screening laboratory tests will be performed locally. Day 1 pre-dose labs and those drawn throughout the study should be analyzed by the central laboratory. Results of clinical laboratory tests performed at Screening must be available prior to dosing.

Unexpected abnormal results on urinalysis should be confirmed by retesting of a new, carefully obtained sample.

The following clinical laboratory tests will be performed:

Table 5.3.7-1: Laboratory Assessments

	Screening Performed by Local Laboratory (Outlined in Table 5.1-1)	Study Visits Performed at Central Laboratory except Urinalysis (Outlined in Table 5.1-2 and Table 5.1-3)
Hematology		
Hemoglobin	X	X
Hematocrit	X	X
Red blood cell count (RBC)	X	X
Total leukocyte count with differential	X	X
Absolute platelet count	X	X
Chemistry		
Aspartate aminotransferase (AST)	X	X
Alanine aminotransferase (ALT)	X	X
Total bilirubin	X	X
Direct bilirubin (done as reflex if total bilirubin is > 2 ULN)	If needed	If needed
Alkaline phosphatase	X	X
Bicarbonate		X
Lactate dehydrogenase (LDH)	X	X
Creatinine	X	X
Blood urea nitrogen (BUN)	X	X
Uric acid	X	X
Glucose (random; fasting or non-fasting)	X	X
Total protein	X	X
Albumin	X	X
Sodium	X	X
Potassium	X	X
Chloride	X	X
Calcium	X	X
Phosphorus	X	X

Table 5.3.7-1: Laboratory Assessments

	Screening Performed by Local Laboratory (Outlined in Table 5.1-1)	Study Visits Performed at Central Laboratory except Urinalysis (Outlined in Table 5.1-2 and Table 5.1-3)
Other		
Follicle stimulating hormone (FSH) - post-menopausal women under age 55 only (Refer to Appendix 1)	X	
Urine Pregnancy Test - WOCBP only (if positive reflex to serum)	X	X
Coagulation - Screening Only		
International normalized ratio (INR)	X	Will be done by Central Lab only if part of DILI Reflex
Activated partial thromboplastin time (aPTT)	X	
Prothrombin time (PT)	X	Will be done by Central Lab only if part of DILI Reflex
Urinalysis - Urinalysis Testing specified below is to be done locally for all time points		
Protein	X	X (done locally)
Glucose	X	X (done locally)
Blood	X	X (done locally)
Leukocyte esterase	X	X (done locally)
Specific gravity	X	X (done locally)
pH	X	X (done locally)
Microscopic Examination - A full microscopic examination	X	X (done locally)
Serology - Central Lab Only Done as part of DILI reflex		
HepA antibody		Will be done by Central Lab only if part of DILI Reflex
HepB surface antigen		Will be done by Central Lab only if part of DILI Reflex
HepC antibody		Will be done by Central Lab only if part of DILI Reflex

Results of all laboratory tests required by this protocol must be provided to BMS, either recorded on the laboratory pages of the CRF or by another mechanism as agreed upon between the

investigator and BMS (eg, provided electronically). If the units of a test result differ from those printed on the CRF, the recorded laboratory values must specify the correct units. Any abnormal laboratory test result considered clinically significant by the investigator must be recorded on the appropriate AE page of the CRF (see [Section 6.3](#)) and evaluated as clinically indicated.

5.3.7.1 Renal Impairment

The exclusion and discontinuation criteria for severe renal impairment should be evaluated based on eGFR calculated by the local laboratory. In the event that eGFR is not reported by the local laboratory, it should be calculated by the Modification of Diet in Renal Disease (MDRD) Study Equation.

$$\text{eGFR} = 186 * \text{serum creatinine mg/dL}^{-1.154} * \text{Age}^{-0.203} [*0.742 \text{ if female}] [*1.212 \text{ if African American}]$$
^{6,7}

5.3.8 Other Supplemental (Unscheduled) Visits

At any time during the trial, the investigator may at his/her discretion arrange for a subject to have an unscheduled (supplemental) assessment(s), especially in the case of AEs that require follow-up. If a subject is seen for an unscheduled assessment, the appropriate Supplemental Pages of the eCRF must be completed.

5.4 Efficacy Assessments

The primary efficacy endpoint of the study is the incidence of a composite of symptomatic ischemic stroke by Day 28 and unrecognized brain infarction assessed by MRI at Day 28. Symptomatic stroke is defined in [Section 5.4.1](#). Unrecognized brain infarction is defined in [Section 5.4.2](#).

Additional secondary efficacy endpoints include Major Adverse Cardiovascular Events (MACE), including symptomatic stroke, myocardial infarction, and cardiovascular death. Myocardial infarction is defined in [Section 5.4.3](#). Classification of deaths is described in [Section 5.4.4](#).

5.4.1 Symptomatic Stroke

All cases of suspected recurrent stroke will be adjudicated by a blinded Clinical Events Adjudication Committee (CEC). Further information regarding the CEC and its processes are detailed in the CEC Charter.

Diagnosis of stroke will require the abrupt onset of focal neurological symptoms lasting at least 24 hours or identification of an acute, new infarct by CT or MRI in subjects with symptoms lasting less than 24 hours. Evaluation and treatment of strokes will be according to the local standard of care. It is strongly recommended (but not required) that an imaging procedure such as a CT scan or MRI be performed to evaluate events of suspected stroke or TIA. Adjudicated strokes will be categorized by the CEC as definite ischemic, definite hemorrhagic, hemorrhagic transformation or type uncertain. Additional classification of stroke subtypes will be specified in the CEC charter.

Evaluation of suspected TIA events should be performed according to the local standard of care. If a TIA is considered to be a suspected stroke event by the investigator, the procedure for reporting a suspected stroke event should be followed and the event will be adjudicated.

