7.2 Independent Central Adjudication Committees

The clinical events adjudication committee (CEC) will be a blinded, independent group of clinicians experienced in the diagnosis of stroke and other cardiovascular diseases who are not otherwise involved with the study. The CEC will evaluate clinical events related to study endpoints, including adjudication of suspected symptomatic stroke, suspected myocardial infarction, bleeding, and death. The full role of the CEC and criteria for evaluation of clinical events will be defined in the CEC charter.

The imaging adjudication committee (IAC) will be an independent group of neuroradiologists experienced in the interpretation of brain MRI images. The IAC will evaluate blinded MRI images obtained no later than 24 hours after randomization and at the Day 28 study visit for detection of unrecognized brain infarctions. The full role of the IAC and criteria for evaluation of unrecognized brain infarction will be defined in the IAC charter.

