4.1.1 Symptomatic Stroke

All cases of suspected recurrent stroke will be adjudicated by a blinded Clinical Events Adjudication Committee (CEC). Diagnosis of stroke will require the abrupt onset of focal

neurological symptoms lasting at least 24 hours. Evaluation and treatment of strokes will be according to the local standard of care. It is strongly recommended (but not required) that an imaging procedure such as a CT scan or MRI be performed to evaluate events of suspected stroke or TIA.

Adjudicated strokes will be categorized by the CEC as definite ischemic, definite hemorrhagic, hemorrhagic transformation or type uncertain. Additional classification of stroke subtypes will be specified in the CEC charter.

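### Transient episodes reach the adjudication committee only on the site's label, and protocol and SAP disagree on whether they can be strokes, so some symptomatic-stroke and MACE events can go uncounted

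*Protocol*

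**What the plan says.** **Definition.** Protocol 5.4.1 gives two routes to a stroke: focal symptoms of at least 24 hours, or "identification of an acute, new infarct by CT or MRI in subjects with symptoms lasting less than 24 hours". SAP 4.1.1 keeps only the first, "neurological symptoms lasting at least 24 hours", and has no imaging route.

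**Work-up.** Protocol 5.4.1 states: "Evaluation of suspected TIA events should be performed according to the local standard of care". On imaging of a suspected stroke or TIA it says: "It is strongly recommended (but not required) that an imaging procedure such as a CT scan or MRI be performed".

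**Referral.** The last sentence of Protocol 5.4.1 sets the condition for sending a TIA to the committee: "If a TIA is considered to be a suspected stroke event by the investigator". Only then is it to be reported as a suspected stroke and adjudicated. Protocol 7.2 describes the CEC's work as "including adjudication of suspected symptomatic stroke, suspected myocardial infarction, bleeding, and death"; TIA is not named.

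**What is counted.** Protocol 8.4 and SAP 7.5 base the primary and secondary analyses on adjudicated events.

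**MRI.** Every subject has a baseline and a Day 28 study MRI, both read centrally by the Imaging Adjudication Committee (Protocol 5.4.2). The central result is not returned to sites (Protocol 5.3.1). Tables 5.1-2 and 5.1-3 schedule no study MRI after Day 28.

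**The concern.** The imaging route exists for episodes under 24 hours, yet whether such an episode reaches the blinded committee depends on how the site labels it. A site that classifies by duration may record a TIA and stop there, particularly if the local reading missed or discounted a small infarct. Another site may submit the same episode and have it counted as a stroke. The SAP's shorter definition makes uniform labelling harder to assume, because the trial's own documents disagree on whether these episodes are strokes.

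Bleeding is handled differently. Protocol 5.3.2 requires submission on observable grounds: overt bleeding that leads to treatment, evaluation or stopping study medication. Transient neurological episodes have no such trigger.

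At stake are symptomatic stroke by Day 28, MACE by Day 90 and the composite of ischemic stroke, MI and CV death. For episodes after Day 28, the composite of MRI infarction and MACE is also exposed. MACE matters most, as the only secondary endpoint in the sequential testing procedure.

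**Working it through.** The plan states no figure on this point, so the check has three parts: where an unsubmitted event goes, how many subjects could be concerned, and what losing events would do to the MACE test.

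**1. Path of an episode under 24 hours with a new infarct that is not submitted**

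| Endpoint | Episode by Day 28 | Episode after Day 28 |
|---|---|---|
| Primary composite | Usually still counted, as an unrecognized infarction on the Day 28 MRI | Not applicable |
| Symptomatic stroke by Day 28 | Lost | Not applicable |
| MACE by Day 90 | Lost | Lost |
| Ischemic stroke, MI or CV death by Day 90 | Lost | Lost |
| MRI infarction plus MACE | Usually still counted, through the MRI | Lost |

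The MRI protection has two gaps. If the Day 28 MRI is not evaluable and no stroke has been adjudicated, SAP 4.1 sets the primary endpoint to missing. The baseline MRI may be taken up to 24 hours after randomization, so an infarct that occurs before that scan is not new at Day 28. In addition, neither document passes a centrally detected infarct to the CEC when the subject had an earlier transient episode.

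**2. Subjects whose classification depends on the site's label**

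Only the 1312 randomized subjects come from the documents. Two inputs are assumed: the share of subjects with a transient episode by Day 90 (2-5%), and the share of those with an infarct on routine imaging (10-40%).

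Formula: 1312 × episode share × infarct share.

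- Low: 1312 × 0.02 × 0.10 = 2.6
- Middle: 1312 × 0.03 × 0.25 = 9.8
- High: 1312 × 0.05 × 0.40 = 26.2

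This gives about 3 to 26 subjects. No non-referral share has been applied, so these are ceilings under the assumed rates. If 10-50% of the middle case went unreferred (also an assumption), the loss would be 9.8 × 0.10 = 1.0 to 9.8 × 0.50 = 4.9 subjects.

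**3. Effect on the MACE test**

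Power was computed analytically for the SAP's two candidate models on the logit scale, without the study-period covariate. For the primary endpoint (14% placebo rate, 30% maximum reduction, one-sided 0.15) this gives 78.1% with 1240 evaluable subjects and 79.6% with 1312. Both are within 2 points of the stated 80%, so the method is adequate for illustration. The present point does not alter that figure.

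For MACE the assumptions are: placebo rate 4-10%, the primary endpoint's relative reductions, all 1312 analysed, one-sided 0.025, and the same share of events missed in every arm.

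| Placebo MACE | Events, none missed | Power | Events, 10% missed | Power | Events, 30% missed | Power |
|---|---|---|---|---|---|---|
| 4% | 42 | 16% | 38 | 15% | 30 | 12% |
| 6% | 64 | 22% | 57 | 20% | 44 | 16% |
| 8% | 85 | 28% | 76 | 25% | 59 | 21% |
| 10% | 106 | 34% | 95 | 31% | 74 | 25% |

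Equal under-counting leaves the relative risk unchanged. It costs about 1-3 points of power at 10% missed and up to about 9 points at 30% missed, on a test that already has low power under these assumptions.

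**The case against.** The strongest reply is that the protocol, read as a whole, already covers most of these episodes. All suspected recurrent strokes go to the CEC, and an infarct seen on CT or MRI makes a short episode a stroke by definition. A site that sees one therefore has at least a suspected stroke. Protocol 5.3.1 also sends imaging used for suspected endpoints to the committee. This stands. A reader might infer that an investigator must be convinced of a stroke before referring, or that imaged infarcts are never submitted; the text supports neither. The trigger is suspicion. What remains are episodes where the local reading missed or discounted an infarct, and sites that label by duration.

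Second, the CEC charter is not available. It is said to define the committee's full role and may contain a wider trigger, and the list in Protocol 7.2 is introduced as inclusive. That also stands as a limit on certainty. Even so, sites decide what to submit, and they work from the protocol.

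Third, the consequence is limited: the primary endpoint is largely protected, and MACE is formally tested only after the primary passes at one-sided 0.025. This is correct, and it keeps the point on the secondary endpoints.

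**Conclusion.** The gap is real and falls on secondary endpoints. Protocol 5.4.1 makes certain short episodes strokes but leaves their submission to the site's suspicion, and SAP 4.1.1 contradicts the protocol on the same episodes. If the committee works to the SAP wording, even submitted episodes could be rejected; if it works to the protocol wording, the SAP sentence is simply wrong. The two must be reconciled in either case.

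The size is unknown, because the documents give no TIA or MACE rate. The 3 to 26 subjects rest on the assumed rates and bound the loss under them, since many such episodes would be referred.

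Two stronger readings are not supported. A reader might set the middle case of 9.8 subjects against an assumed overall MACE rate of 6% (0.06 × 1312 = 79 events) and conclude that 12% of MACE events will be lost. That ratio uses three assumed inputs and no non-referral share, so it is the ceiling of one scenario. The low and high cases give about 3% and 33%. With 10-50% of the middle case unreferred, the ratio is about 1-6%. A reader might also infer bias between arms. Sites are blinded, so the expected harm is lost events and inconsistency between sites.

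**What to change.** 1. In Protocol 5.4.1, replace the investigator-dependent sentence with a rule that all suspected TIA events through Day 90 are submitted to the CEC with any imaging already obtained, and that the CEC decides whether the stroke definition is met.
2. Name suspected TIA among the events for adjudication in Protocol 7.2, and make the CEC charter consistent if it is not already.
3. Align the definition in SAP 4.1.1 with Protocol 5.4.1.

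**Cost.** If 2-5% of subjects have a TIA, the existing committee receives 1312 × 0.02 = 26 to 1312 × 0.05 = 66 dossiers for such events; some would be submitted anyway. Extending the rule to all transient neurological events would bring in more. No new imaging or visits are needed. The protocol change requires an amendment with ethics approval (Protocol 9.1.1), and SAP 2.2 shows that enrolment was under way when it was written. Adverse events are collected at every contact through follow-up, so earlier reported episodes can be looked for in those records.

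**Limit.** Episodes that were never imaged will still not be classifiable under the imaging route.
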